13.9 Retention of Data

The investigator shall retain and preserve 1 copy of all data generated in the course of the study, specifically including but not limited to those defined by GCP as essential, for the longer of: (a) 2 years after the last marketing authorization for the investigational test article has been approved or the sponsor has discontinued its research with respect to such investigational test article or (b) such longer period as required by applicable global regulatory requirements. At the end of such period, the investigator shall notify the sponsor in writing of its intent to destroy all such material. The sponsor shall have 30 days to respond to the investigator's notice, and the sponsor shall have a further opportunity to retain such materials at the sponsor's expense.

13.10 Publication and Disclosure Policy

The sponsor assures that the key design elements of this protocol will be posted in a publicly accessible database such as clinicaltrials.gov. In addition, upon study completion and finalization of the study report, the results of this study will be submitted for publication and/or posted in a publicly accessible database of clinical study results.

Upon completion of the study, the investigator may publish the results in recognized (refereed) scientific journals subject to the provisions of the CSA. Unless otherwise specified in the CSA, the following process shall occur:

The institution and principal investigator (PI) shall not publish or present data from an individual study center until the complete multi-center study has been presented in full or for 2 years after the termination of the multi-center study, whichever occurs first. Subsequent publications must refer to the multi-center findings. Thereafter, if the PI expects to participate in the publication of data generated from this site, the institution and PI shall submit reports, abstracts, manuscripts, and/or other presentation materials to the sponsor for review before submission for publication or presentation. The sponsor shall have 60 days to respond with any requested revisions, including, without limitation, the deletion of confidential information. The PI shall act in good faith upon requested revisions, except that the PI shall delete any confidential information from such proposed publication. The PI shall delay submission of such publication or presentation materials for up to an additional 90 days to have a patent application(s) filed.

Appendix 1 Schedule of Assessments

Study Phase	Screening	Double-Blind Treatment					Follow-up
		Day 1 Baseline ^b	Day 14 Tele-visit ^c	Day 28	Day 56	Day 84/EOT	
Visit Name	Screening ^a						30 Day Safety Follow-up Call ^d
Visit Window	N/A	N/A	± 2d	± 3d	± 3d	+5d /- 2d	+ 7d
Informed consent ^e	X						
Inclusion/exclusion criteria	X	X					
Medical history/current medical conditions	X						
Demography	X						
Physical examination	X					X	
Height	X						
Weight	X	X		X	X	X	
BMI	X						
Serum or urine pregnancy test ^f	X	X		X	X	X	
Vital signs (BP, HR, body temperature, and pulse oximetry) ^g	X	X		X	X	X	
Hematology ^h	X	X		X		X	
Serum chemistry	X	X		X		X	
Biomarkers (serum, plasma) ⁱ		X				X	
Sputum collection for microbiology ^j	X ^k	X		X	X	X	
CT scan of chest	X ^l					X	
12-lead ECG	X					X	
NTM Symptom Assessment Questionnaire	X	X		X	X	X	
St. George's Respiratory Questionnaire (SGRQ)		X		X	X	X	

Study Phase	Screening	Double-Blind Treatment					Follow-up
Visit Name	Screening ^a	Day 1 Baseline ^b	Day 14 Tele-visit ^c	Day 28	Day 56	Day 84/EOT	30 Day Safety Follow-up Call ^d
Visit Window	N/A	N/A	± 2d	± 3d	± 3d	+5d /- 2d	+ 7d
Quality of Life – Bronchiectasis (QOL-B)		X		X	X	X	
PROMIS-Fatigue Short Form 7a		X		X	X	X	
Patient Global Impression – Severity (PGI-S)		X		X	X	X	
Patient Global Impression – Change (PGI-C)				X	X	X	
Clinical Global Impression – Severity of Illness (CGI-S)		X		X	X	X	
Clinical Global Impression - Global Improvement Scale (CGI-I)				X	X	X	
Dispense test article		X		X	X		
Test article administration ^m		X	◀	▶	X		
Test article accountability and compliance				X	X	X	
Adverse events ⁿ	X	X	X	X	X	X	X
Prior/concomitant medications ^o	X	X	X	X	X	X	X

β-hCG = serum β-human chorionic gonadotropin; BMI = body mass index; BP = blood pressure; CT = computed tomography; d = day(s); ECG = electrocardiogram; eCRF = electronic case report form; EOT = end of treatment; HR = heart rate; ICF = informed consent form; MABc = *Mycobacterium abscessus* complex; MAC = *Mycobacterium avium* complex; N/A = not applicable; NTM = nontuberculous mycobacterial

- Screening period may occur for up to 8 weeks prior to randomization to allow for sputum microbiology results. Screening procedures may occur on separate days. Subjects may be randomized as soon as all screening procedures have been performed and results have been received to verify eligibility criteria.
- All Day 1/Baseline Visit procedures should be completed prior to subject dosing.
- Day 14 visit will be performed remotely via telephone to assess safety.
- A Safety Follow-up call will be performed 30-37 days after the subject's last dose of test article. At the investigator's discretion, the safety follow-up can be an office visit.
- Written and signed ICF must be obtained before any study-related assessment is performed.
- All female subjects will have a local urine or serum pregnancy test at Screening and at the Baseline Visit. Results will be used to confirm eligibility. In addition, blood will be collected for a serum β-hCG pregnancy test to be sent to the Central Laboratory at the Day 28 and Day 84/EOT visits. At Day 56

visit, a local urine or serum β -hCG pregnancy test may be performed. If Day 56 local pregnancy test results are positive, a serum β -hCG pregnancy test will be sent to the Central Laboratory for confirmation.

- g. Vital signs should be captured after at least 5 minutes (+ 5 minutes) of rest while in a non-standing position (supine or sitting). Subsequent vital sign measurements should be captured in the same non-standing position.
- h. Hematology includes coagulation.
- i. Serum and plasma for biomarkers will be collected and stored for future use for all subjects who agree to provide samples during the consenting process.
- j. Specimens may be obtained via spontaneous sputum expectoration or sputum induction. Approximately 5 mL of sputum should be collected per sample. To improve the probability of obtaining a good sputum specimen, at least 2 and preferably 3 spontaneously expectorated sputum samples will be obtained from subjects at each timepoint. Specimens should be collected by the subject on 2 to 3 consecutive days (when possible), just prior to, and up through the day of the scheduled study visit. If a subject is unable to produce sputum spontaneously and independently, sputum induction may be performed by appropriately qualified site staff to obtain one induced sputum specimen.
- k. To be eligible for participation, subjects must have at least 1 prior positive culture for MABc in the 6 months prior to Screening, and 1 positive culture at Screening (note: the prior cultures and Screening cultures must be at least 30 days apart). At least 2 and preferably 3 spontaneously expectorated sputum samples (approximately 5 mL each) should be collected on 2 to 3 consecutive days (when possible) during the week following the subject signing informed consent.
- l. May utilize results of chest CT scan performed within 3 months prior to Screening to determine eligibility (radiographic evidence of MABc infection). If no CT scan was obtained within prior 3 months, CT scan to be performed at Screening. High resolution CT scan is preferred, if available.
- m. All doses will be taken orally, once daily in a fasted state. Fasting is defined as no food, antacids or multivitamins containing multivalent cations (eg, aluminum, magnesium, calcium, bismuth, iron, or zinc) or drink except water for at least 4 hours before dosing. After dosing, no food for 2 hours, no dairy products, antacids or multivitamins containing multivalent cations (eg, aluminum, magnesium, calcium, bismuth, iron, or zinc) for 4 hours.
- n. Adverse events will be reported and recorded from signing of ICF through the Follow-up call.
- o. All antibiotics administered for the subject's MABc or MAC infection within 2 years prior to the date of informed consent will be recorded in the eCRF. All significant non-pharmacological therapies related to MABc infection including patient education, airway clearance technique, inspiratory muscle training and exercise training administered from 30 days prior to date of informed consent, and administered throughout the duration of the study through the 30-day follow-up period, will be recorded in the eCRF. All pharmacological therapies (regardless of indication) that have been administered from 7 days prior to the date of informed consent and administered throughout the duration of the study through the 30-day follow-up period, will be recorded in the eCRF. All significant non-pharmacological therapies not related to MABc infection administered from 7 days prior to date of informed consent, and administered throughout the duration of the study through the 30-day follow-up period, will be recorded in the eCRF.

Appendix 2 Equations and Conversion Factors

1. Cockcroft-Gault equation to calculate creatinine clearance (relevant to Exclusion Criterion number 6):

$$\frac{(140-\text{age [yrs]}) * \text{weight (kg)} * (Z)}{\text{Cr (mg/dL)} * 72}$$

Z = 1.0, if Male
Z = 0.85, if Female

2. Corticosteroid conversions (relevant to Exclusion Criterion number 5):

	Approximate equivalent dose ^a (mg)	Relative glucocorticoid activity	Relative mineralocorticoid activity	Duration of action (hours)
Glucocorticoids				
Short-acting				
Hydrocortisone	20	1	1	8-12
Cortisone	25	0.8	0.8	8-12
Intermediate-acting				
Prednisone	5	4	0.8	12-36
Prednisolone	5	4	0.8	12-36
Methylprednisolone	4	5	Minimal	12-36
Triamcinolone	4	5	0	12-36
Long-acting				
Dexamethasone	0.75	30	Minimal	36-72
Betamethasone	0.6	30	Negligible	36-72
Mineralocorticoids				
Fludrocortisone	^b	10-15	125-150	12-36

^a Equivalent dose shown is for oral or IV administration. Relative potency for intra-ocular or intramuscular administration may vary considerably.

^b Glucocorticoid doses which provide a mineralocorticoid effect that is approximately equivalent to 0.1 mg of fludrocortisone are: prednisone or prednisolone 50 mg, or hydrocortisone 20 mg.

Source: [Liu 2013](#)

Appendix 3 Sputum Induction Guidelines

Introduction

Collection of adequate sputum samples (approximately 5 mL) is critical. Sputum samples will be collected by the subject (at home) and/or at the study site. In the event the subject is unable to spontaneously expectorate the required volume of sputum, induction may be performed at the study site by qualified site staff. This guidance document is intended to provide recommendations for obtaining an adequate sputum sample via sputum induction.

Recommended Equipment

- Standard handheld nebulizer – thoroughly cleaned and disinfected
- Sputum specimen containers with labels
- Sputum collection tubes (provided by the Central Laboratory)
- Hypertonic sodium chloride solution (at minimum 3%, plus 5% and 7% if needed)
- Other clinic supplies (eg, disinfectant/germicidal/alcohol wipes, gloves, masks, tissues, paper towels, etc.)

CONTRAINDICATIONS TO SPUTUM INDUCTION

- This procedure should not be performed in subjects in which severe coughing may be harmful, such as subjects with:
 - Recent or recurrent hemoptysis
 - Acute respiratory distress
 - Acute hypoxia (SaO_2 in room air of < 90%)
 - Known pneumothorax
 - Rib fractures or chest wall musculoskeletal injury
 - Unstable cardiac conditions
 - Recent eye surgery

Instructions:

Preparation

- Subjects should be instructed not to eat at least 1 hour prior to sputum induction.
- Subjects should be informed of the purpose of this procedure before commencing.
- The procedure should be discussed with the subject:
 - They will experience a salty taste in their mouth
 - They may cough
 - They will likely produce lung secretions that they will need to expectorate
 - If they have pre-existing hyperreactive airways eg, asthma, they will receive pre-medication with an inhaled bronchodilator
- Sputum induction should occur in a private, contained room, following clinic processes to ensure sterilization and prevent contamination.
- Site staff performing induction should wear gloves and an N95 mask for the duration of the procedure.

- All collection containers should have a sputum collection label completed with subject identifiers (ie: subject #, visit ID, collection date and time).
- The induction procedure should start with using lower concentrations of saline (eg, 3%) as per the investigator's discretion. Approximately 3-6 mL of hypertonic saline should be placed in the nebulizer.
- Subjects should be sitting up or in a semi-fowler position.

Nebulization

- Nebulization time is approximately 10 minutes in total, with breaks in nebulization at 5-minute intervals or if the patient has respiratory distress, excessive coughing.
- Nebulization may extend to 15 minutes if the patient is in no distress and more sputum needs to be collected.
- Nebulization should stop at 15 minutes total time, even if inadequate sputum is collected.
- The saline concentration may be increased to a maximum of 7% per investigator discretion.
- Subjects should be instructed to breathe slowly and deeply (pausing at peak inspiration) through the nebulizer mouthpiece inhaling the saline mist.
- If the subject needs to expectorate during nebulization, turn off the nebulizer and allow the subject to expectorate into the container.
 - If a sufficient specimen is collected, procedure can stop.
 - If an insufficient volume of sputum is collected, the subject should resume the nebulization treatment and complete the full 15-minute duration in three 5-min intervals.
- Subjects should be encouraged to blow their nose as needed during the induction to help prevent nasal secretions from becoming mixed with the sputum specimen.
- Upon completion, subjects should take a few deep breaths, swallow the extra saliva in their mouth and attempt to forcefully cough up a sputum sample into a sputum container. The container should be closed immediately after the appropriate volume of sputum (approximately 5 mL) is collected.
- Closely monitor the subject for tolerability issues or side effects.
- The sputum sample should be refrigerated until it is sent to the central specialty microbiology laboratory.
- Please refer to the Central Laboratory Manual for further instructions on packaging and shipping specimens to the lab.

Appendix 4 NTM Symptom Questionnaires

NTM Symptom Assessment Questionnaire – Baseline (Day 1) Visit

PART 1:

Instructions: Please indicate if you have experienced any of the following twelve symptoms within the past 7 days by using the scale below (Absent, Mild, Moderate or Severe). Please rate your overall impression of each symptom within the past 7 days. **Please circle one response for each symptom.**

	SYMPTOM			
	ABSENT	MILD	MODERATE	SEVERE
Cough	ABSENT	MILD	MODERATE	SEVERE
Coughing up blood	ABSENT	MILD	MODERATE	SEVERE
Wheezing	ABSENT	MILD	MODERATE	SEVERE
Chest pain	ABSENT	MILD	MODERATE	SEVERE
Throat clearing	ABSENT	MILD	MODERATE	SEVERE
Mucus (sputum) production	ABSENT	MILD	MODERATE	SEVERE
Shortness of breath	ABSENT	MILD	MODERATE	SEVERE
Fatigue	ABSENT	MILD	MODERATE	SEVERE
Fever	ABSENT	MILD	MODERATE	SEVERE
Night sweats	ABSENT	MILD	MODERATE	SEVERE
Poor appetite	ABSENT	MILD	MODERATE	SEVERE
Weight loss	ABSENT	MILD	MODERATE	SEVERE

PART 2:

Instructions: From the list of symptoms above, please indicate up to (3) symptoms which are most bothersome for you by ranking in order from most bothersome (#1) to least bothersome (#3).

1. _____

2. _____

3. _____

NTM Symptom Assessment Questionnaire – All Other Visits

Please indicate which visit the questionnaire is being completed at:

- Screening
- Day 28 Visit
- Day 56 Visit
- Day 84 Visit

Instructions: Please indicate if you have experienced any of the following twelve symptoms within the past 7 days by using the scale below (Absent, Mild, Moderate or Severe). Please rate your overall impression of each symptom within the past 7 days. Please circle one response for each symptom.

	SYMPTOM			
	ABSENT	MILD	MODERATE	SEVERE
Cough	ABSENT	MILD	MODERATE	SEVERE
Coughing up blood	ABSENT	MILD	MODERATE	SEVERE
Wheezing	ABSENT	MILD	MODERATE	SEVERE
Chest pain	ABSENT	MILD	MODERATE	SEVERE
Throat clearing	ABSENT	MILD	MODERATE	SEVERE
Mucus (sputum) production	ABSENT	MILD	MODERATE	SEVERE
Shortness of breath	ABSENT	MILD	MODERATE	SEVERE
Fatigue	ABSENT	MILD	MODERATE	SEVERE
Fever	ABSENT	MILD	MODERATE	SEVERE
Night sweats	ABSENT	MILD	MODERATE	SEVERE
Poor appetite	ABSENT	MILD	MODERATE	SEVERE
Weight loss	ABSENT	MILD	MODERATE	SEVERE

Appendix 5

Sponsor Signature

Adverse Events and Concomitant Medications	34	
Standard Calculations	35	
APPENDIX B: SAS PROGRAMMING QUALITY CONTROL REQUIREMENTS		36
APPENDIX C: TABLE, FIGURE, LISTING LAYOUTS		37
APPENDIX D: DMID ADULT TOXICITY TABLE		38
APPENDIX E: DIRECTIONALITY OF WORST LABORATORY PARAMETERS		39

LIST OF ABBREVIATIONS AND DEFINITIONS OF TERMS

Abbreviation	Definition
AE	adverse event
ANCOVA	analysis of covariance
ATC	Anatomical Therapeutic Chemical
BMI	body mass index
CGI-I	Clinical Global Impression - Improvement
CGI-S	Clinical Global Impression - Severity
CSR	clinical study report
ECG	electrocardiogram
eCRF	electronic case report form
EOT	end of treatment
ICE	intercurrent event
ICH	International Council for Harmonisation of Technical Requirements for Pharmaceuticals for Human Use
ITT	intent-to-treat
LS	least squares
MABC	mycobacterium abscessus complex
MAC	mycobacterium avium complex
MedDRA	Medical Dictionary for Regulatory Activities
MIC	Minimum Inhibitory Concentration
NTM	nontuberculous mycobacterial
OR	odds ratio
PCS	potentially clinically significant
PGI-C	Patient Global Impression of Change
PGI-S	Patient Global Impression of Severity
PP	per-protocol
PROMIS	Patient-reported Outcomes Measurement Information System
PT	preferred term
QC	quality control
QOL-B	Quality of Life – Bronchiectasis
QTc	corrected QT interval
QTcF	corrected QT interval according to Fridericia's formula
SAP	statistical analysis plan
SGRQ	St Georges Respiratory Questionnaire
SOC	system organ class
TEAE	treatment-emergent adverse event

Abbreviation Definition

TLFs	tables, listings, and figures
WHO	World Health Organization

1. INTRODUCTION

This document outlines the statistical methods to be implemented during the analyses of data collected within the scope of Study PTK0796-NTM-20203 (A Phase 2, Double-Blind, Randomized, Parallel-Group, Placebo-Controlled, Multi-Center Study to Evaluate the Efficacy, Safety, and Tolerability of Oral Omadacycline in Adult Subjects with Nontuberculous Mycobacterial [NTM] Pulmonary Disease Caused by *Mycobacterium abscessus* Complex [MABC]). The purpose of this statistical analysis plan (SAP) is to provide specific guidelines for the statistical analyses. Any deviations from this plan will be documented in the clinical study report (CSR).

2. STUDY DOCUMENTS

The following study documents are used for the preparation of the SAP:

- Protocol, version 2.0, 06-Dec-2021
- Annotated electronic case report form (eCRF), version 2.0, 01Feb2022.

3. STUDY OBJECTIVES

3.1 Primary Objectives

Efficacy: To evaluate the efficacy of omadacycline in adult subjects with NTM pulmonary disease caused by MABC based upon subject assessment of symptoms.

Safety: To evaluate the safety and tolerability of omadacycline in adult subjects with NTM pulmonary disease caused by MABC.

3.2 Secondary Objectives

The secondary objectives of the study are:

- To evaluate patient-reported outcomes and quality of life in adult subjects with NTM pulmonary disease caused by MABC
- To evaluate the microbiological response of omadacycline in adult subjects with NTM pulmonary disease caused by MABC

[figure not shown]
4. STUDY DESIGN AND PLAN

This is a Phase 2, double-blind, randomized, placebo-controlled, parallel-group, multicenter study in adults with NTM pulmonary disease caused by MABC.

Following a Screening period of up to 56 days (8 weeks) prior to dosing, eligible subjects will be randomized (1.5:1) to receive either 300 mg once daily oral omadacycline monotherapy or matching placebo.

Subjects will attend monthly visits during the approximately 84 day (3-month) double-blind treatment period and will complete a 14-day safety tele-visit as well as a safety follow-up call approximately 30 days after their last dose of test article (See Figure 1).

Figure 1. Study schema, protocol amendment v2.0, 06-Dec-21

Following an estimated recruitment period of approximately 24 months, the total duration of subject participation in the study is approximately 5 months which includes a total duration of study treatment for approximately 3 months (84 days).

5. DETERMINATION OF SAMPLE SIZE

As the study is exploratory with respect to determination of efficacy, the sample size determination is provided to better ensure sufficient subjects are enrolled to provide an initial assessment of efficacy rather than test a specific hypothesis. With a randomization ratio of 1.5:1, a sample size of 75 subjects (45 omadacycline and 30 placebo) will provide approximately 80% power to detect an absolute treatment difference of 30% in clinical response rate at Day 84, based on clinical response rates of 15% and 45% in the placebo and omadacycline treatment groups respectively, using a Mantel-Haenszel test with 2-sided alpha level of .05.

6. GENERAL ANALYSIS CONSIDERATIONS

The statistical analyses will be reported using summary tables, listings, and figures (TLFs). The International Council for Harmonisation of Technical Requirements for Pharmaceuticals for Human Use (ICH) numbering convention will be used for all TLFs. Unless otherwise noted, all p-values will be 2-sided. No adjustments for multiplicity will be made in this study, and any p-values presented are not testing pre-specified inferential hypotheses.

Continuous variables will be summarized by presenting the number of observations, means, SDs, medians, minimums, and maximums. Other summaries (e.g., quartiles, 5%, 95% CIs) may be used as appropriate.

Categorical variables will be summarized by presenting counts and percentages of subjects in corresponding categories. All possible categories as defined in the eCRF should be populated, even if they have zero counts. Percentages are based on the total number of subjects (N) for a given treatment and population, unless otherwise specified.

All summary tables will be presented by treatment group. Baseline summaries will also include a total summary column.

Individual subject data obtained from the eCRFs, external vendors, central clinical laboratory, central electrocardiogram (ECG) laboratory, and selected derived data will be presented by subject in data listings.

The analyses described in this plan are considered a priori, in that they have been defined before breaking the blind.

Any analyses performed after breaking the blind will be considered post hoc and exploratory. Post hoc analyses will be labeled as such on the output and identified in the CSR.

All analyses and tabulations will be performed using SAS® statistical software, version 9.4 or higher (SAS Institute Inc). TLFs will be presented in rich text format (RTF) and/or PDF.

The process for SAS program validation and quality control (QC) for programs and outputs is documented in the Synteract working instruction “SAS Programming Quality Control”. Study-specific QC requirements can be found in APPENDIX B: SAS PROGRAMMING QUALITY CONTROL REQUIREMENTS.

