8. ANALYSIS SETS

The following subject population will be used for safety analyses:

- The safety analysis set will include all subjects who received at least 1 dose of test article. Treatment assignment will be based on the actual test article received the majority of time while on treatment.

The following subject populations will be used for efficacy analyses:

- The intent-to-treat (ITT) analysis set will include all randomized subjects. Treatment assignment will be based on the randomized treatment.
- The per-protocol (PP) analysis set will include all randomized subjects who received at least 1 dose of test article and completed the study without major protocol deviations that affect the assessment of efficacy. The decision whether a subject is excluded from the PP analysis set will be made prior to database lock and unblinding. Treatment assignment will be based on randomized treatment.

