11.4 Handling of Dropouts or Missing Data

Data imputation methods for the primary endpoint and other analyses for the primary endpoint are described in Section 11.1.

No imputations will be made for missing values for secondary endpoints. Summaries for these endpoints will be based on observed data only.

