13.3 Clinical Laboratory Evaluation

Laboratory parameters (serum chemistry, hematology, and coagulation) will be summarized using descriptive statistics at baseline and at each post-baseline time point (the Day 28 and 84 visit, Day84/EOT) and for the most extreme (high and/or low) post-baseline value at any visit (including unscheduled results). Changes from baseline will also be summarized.

Select laboratory parameters will be graded according to the Division of Microbiology and Infectious Diseases (DMID) grading criteria, version 5.0. Incidence of potentially clinically significant (PCS) events (at least a 2-grade increase from baseline) will be presented by time point and for the most extreme post-baseline value at any visit (including unscheduled results).

The number and percentage (based on the number of subjects with a normal level at baseline) of subjects in each treatment group with an elevated transaminase (AST or ALT) level ($> 3 \times$ upper limit of normal [ULN], $> 5 \times$ ULN, and $> 10 \times$ ULN), an elevated bilirubin level ($> 1.5 \times$ ULN and $> 2 \times$ ULN) will be presented by study visit and at any post-baseline visit. A listing of subjects who meet the laboratory criteria for Hy's law at the same visit will also be provided. The laboratory criteria for Hy's law are defined as 1) ALT or AST $> 3 \times$ ULN, ALP $\leq 2.0 \times$ ULN, and total bilirubin > 1.5 ULN and 2) ALT or AST $> 3 \times$ ULN, ALP $\leq 2.0 \times$ ULN, and total bilirubin $> 2 \times$ ULN.

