13.4 Vital Signs

Vital signs (systolic blood pressure, diastolic blood pressure, heart rate, pulse oximetry, and temperature) and weight will be summarized using descriptive statistics at baseline and at each post-baseline time point (the Day 28, 58 and 84 visit and Day 84/EOT) as well as for the most extreme result (high and low). Changes from baseline will also be summarized.

Incidence of PCS events will be presented by time point and for the most extreme post-baseline value at any visit (including unscheduled results).

Table 12.4 Vital Sign PCS Thresholds

Criteria for Treatment Emergent PCS Vital Signs

Vital Sign Parameter	Flag	Criterion Value	Change from Baseline
Systolic Blood Pressure (mmHg)	High (CH)	≥ 180	Increase of ≥ 20 mmHg
	Low (CL)	≤ 90	Decrease of ≥ 20 mmHg
Diastolic Blood Pressure (mmHg)	High (CH)	≥ 105	Increase of ≥ 15 mmHg
	Low (CL)	≤ 50	Decrease of ≥ 15 mmHg
Heart Rate (bpm)	High (CH)	≥ 120	Increase of ≥ 15 bpm
	Low (CL)	≤ 50	Decrease of ≥ 15 bpm
Temperature (°C)	Low (CL)	<36.0	NA
	High (CH)	>38.0	NA

bpm=beats per minute; C=Celsius; DBP=diastolic blood pressure; SBP=systolic blood pressure

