13.6 Electrocardiogram

Overall interpretation results for ECGs will be summarized using shift tables (normal, abnormal not clinically significant, and abnormal clinically significant) comparing baseline to EOT.

Descriptive statistics at baseline and at each post-baseline time point (the Day 84 visit, and Day 84/EOT), as well as changes from baseline, will be summarized for each ECG parameter (ventricular rate, RR, PR, QRS, QT, QTcF).

In addition, a categorical summary of abnormal corrected QT interval (QTc) values will be presented. At each time point, the number of subjects with QTc according to Fridericia's formula ($QTcF = QT/(RR^{1/3})$ (seconds)) and exceeding the thresholds below will be presented.

Table 12.6 ECG PCS Thresholds

ECG Parameter	PCS threshold
QTc (high), unadjusted and Fridericia's	>450 msec
	>480 msec
	>500 msec
QTc (increase), unadjusted and Fridericia's	>30 msec from baseline
	>60 msec from baseline

Source is ICH E14 ECG QTcF category thresholds.

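### By-visit laboratory and vital-sign PCS percentages default to all treated subjects, so anyone with no value at that visit dilutes the rate

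*SAP*

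**What the plan says.** SAP section 6 gives the default: "Percentages are based on the total number of subjects (N) for a given treatment and population, unless otherwise specified". Section 8 fixes what N means for safety: "The safety analysis set will include all subjects who received at least 1 dose of test article". No post-baseline measurement is required.

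The by-visit PCS summaries do not depart from that default:

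- Laboratory tests, 13.3: "Incidence of potentially clinically significant (PCS) events (at least a 2-grade increase from baseline) will be presented by time point". The post-baseline visits are Day 28 and Day 84, plus a combined Day 84/EOT row.
- Vital signs, 13.4: "Incidence of PCS events will be presented by time point and for the most extreme post-baseline value at any visit". The visits are Day 28, Day 56 and Day 84, plus Day 84/EOT. The section prints Day 58; I read this as the Day 56 visit in the protocol's Schedule of Assessments.

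One table in 13.3 does set its own denominator, the transaminase and bilirubin elevations: "The number and percentage (based on the number of subjects with a normal level at baseline) of subjects in each treatment group". It still does not ask for a result at the visit being summarised.

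Table 7.1.2 separates Day 84 from Day 84/EOT. Only the second includes the visit at which a subject stops treatment early. Protocol 12.6 asks for PCS incidence by timepoint and gives no denominator.

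For secondary efficacy, section 11.4 has a separate rule: "Summaries for these endpoints will be based on observed data only". It does not extend to safety.

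**The concern.** A percentage at a visit should describe the subjects assessed at that visit. Under the section 6 default, an unmeasured subject has the same arithmetic effect as a measured subject with a normal result, although nothing in the SAP classifies such a subject as normal. Every affected rate is then pulled towards zero, and by more in the arm with more missing visits.

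The later visits matter most. Safety is a primary objective, protocol 3.2 describes this as the first clinical trial of omadacycline dosing beyond 14 days, and no data monitoring committee is planned. Day 56 and Day 84 carry the new long-exposure information, and missing values accumulate there. A between-arm difference in abnormality rates could be hidden, or an apparent one created, by attendance alone.

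**Working it through.** **Inputs from the documents.** Planned arm sizes are 45 omadacycline and 30 placebo (SAP section 5). The default denominator is N (section 6), and N is all dosed subjects (section 8). Neither document gives a dropout or missed-visit rate, or an expected PCS rate, so those below are assumptions shown over a range.

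**The plan's own figure.** The only stated design figure is about 80% power for 45% versus 15% response. The pooled response is (45 × 0.45 + 30 × 0.15)/75 = 0.33. The null standard error is √(0.33 × 0.67 × (1/45 + 1/30)) = 0.1108. The alternative standard error is √(0.45 × 0.55/45 + 0.15 × 0.85/30) = 0.0987. Then z = (0.30 − 1.96 × 0.1108)/0.0987 ≈ 0.84, which gives 79.9% power. The figure reproduces, and nothing below depends on it.

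**Formula.** With N dosed, a fraction d unmeasured at the visit and a rate q among those measured, the abnormal count is qN(1 − d). Divided by N, the printed rate is q(1 − d). Divided by the number measured, N(1 − d), it is q.

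**Equal underlying rates, q = 15% in both arms (assumed):**

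| Unmeasured, omadacycline / placebo | Printed, omadacycline | Printed, placebo | Difference (points) |
|---|---|---|---|
| 10% / 10% | 0.15 × 0.90 = 13.5% | 0.15 × 0.90 = 13.5% | 0 |
| 20% / 5% | 0.15 × 0.80 = 12.0% | 0.15 × 0.95 = 14.25% | −2.25 |
| 30% / 10% | 0.15 × 0.70 = 10.5% | 0.15 × 0.90 = 13.5% | −3.0 |
| 10% / 20% | 0.15 × 0.90 = 13.5% | 0.15 × 0.80 = 12.0% | +1.5 |

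The true difference is zero in every row. The sign of the printed difference follows whichever arm has more missing values.

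**Unequal underlying rates, 20% omadacycline and 15% placebo (assumed).** The 5.0-point difference prints as 0.20 × 0.80 − 0.15 × 0.90 = 2.5 points with 20% / 10% unmeasured, and as 0.20 × 0.70 − 0.15 × 0.90 = 0.5 points with 30% / 10%.

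**In counts (assumed).** Omadacycline: 36 of 45 measured, 6 abnormal. Placebo: 27 of 30 measured, 4 abnormal. Among those measured, 6/36 = 16.7% and 4/27 = 14.8%. On N, 6/45 = 13.3% and 4/30 = 13.3%, so the 1.9-point difference disappears.

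**Which rows are exposed.**

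- Laboratory PCS at Day 28 and Day 84, and vital-sign PCS at Day 28, Day 56 and Day 84: exposed.
- Transaminase and bilirubin by visit: exposed in the same way, within subjects normal at baseline.
- Day 84/EOT and most-extreme-value rows: little affected, because early stoppers contribute an EOT or earlier value when they have one.
- QTc thresholds in 13.6: the text asks for a count ("At each time point, the number of subjects with QTc") and names no percentage.
- ECG shift table in 13.6: it compares baseline with EOT, so an early stopper who attends EOT is included.

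**The case against.** The strongest reply is that little information is lost. PCS is also reported at Day 84/EOT and for the most extreme post-baseline value, including unscheduled results, so an abnormality in an early stopper should appear there. Counts and subject listings are provided, so a reader could rebuild the visit rates. No safety hypothesis is tested. In the 20% / 5% case the 2.25-point gap is about one subject in 45 (0.0225 × 45 ≈ 1), while intervals at this sample size are wide: 5/36 has a Clopper-Pearson 95% interval of 4.7% to 29.5%. The table shells are a separate document and might footnote another denominator. All of this limits the importance of the point. It does not change what the SAP instructs for the by-visit rows, and shells that have not been seen cannot be taken to override a stated default.

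Three stronger readings are tempting, and the documents do not support them.

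- **That the rule favours omadacycline.** This needs more missing visits on omadacycline, and no figure is given. Protocol 7.13 and 8.19.5 take subjects who need further antibiotic therapy for worsening disease off test article, which could happen more often on placebo.
- **That ECG percentages are diluted too.** Section 13.6 asks only for QTc counts and a baseline-to-EOT shift, as set out above.
- **That section 6 contradicts the observed-data rule for secondary efficacy.** Section 6 gives way where something else is specified, and 11.4 and 12.2 are most naturally read as specifying it. The CGI scales have no Clopper-Pearson intervals; only PGI-C and PGI-S do. For those two the denominator is implied rather than stated. The choice would matter: 18 improved of 36 observed is 50% (33% to 67%), but 18 of 45 is 40% (26% to 56%).

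**Conclusion.** The point holds for the by-visit laboratory and vital-sign PCS percentages and, in a related form, for the by-visit transaminase and bilirubin table. Applied as written, the plan prints q(1 − d) instead of q. The relative shrinkage equals the unmeasured fraction: 10% unmeasured removes a tenth of the rate, and 30% removes three tenths. Between arms the distortion is zero when missingness and underlying rates are equal. Over the assumed range with q = 15% it runs from 3.0 points in omadacycline's favour to 1.5 points in placebo's.

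This rests on two assumptions: that some dosed subjects lack a value at a scheduled visit, which the separate Day 84 row makes likely once anyone stops early, and that the table shells do not set a different denominator. It is a modest defect in a stated rule and is cheap to correct. Sample size and the primary efficacy analysis are unaffected.

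**What to change.** Add to SAP 13.3 and 13.4:

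1. By-visit categorical percentages use subjects with a value at that visit, and at baseline where the criterion involves change. That n is printed beside each percentage.
2. Most-extreme and any-post-baseline rows use subjects with at least one post-baseline value.
3. The by-visit transaminase and bilirubin percentages use subjects normal at baseline who also have a result at the visit.

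In 12.2.4 and 12.2.5, state that the observed-data rule sets the denominator for the PGI-C and PGI-S percentages and their Clopper-Pearson intervals. This last item is a clarification only.

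The cost is a few sentences and matching table footnotes, with no new data collection. There is one limit: if subjects stop because of an abnormality, a rate among those still measured can also understate risk. The by-visit rows should therefore be read together with the Day 84/EOT and most-extreme rows, which the SAP already plans.
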